7.2. Inclusion Criteria

1. The patient has completed the final treatment study visit of the lead-in study and is judged by the investigator as reasonably compliant, with at least 60% compliance with study medication usage (based on drug accountability).
2. The patient has provided written informed consent to participate in this extension study.
3. The patient met all prior inclusion and exclusion requirements for the double-blind lead-in study, or the site received medical monitor approval for the patient to remain in the lead-in study after the retrospective discovery of an entry violation that did not pose any threat to the patient's safety or well-being.
4. During the course of the lead-in study, the patient has had no intervening medical conditions including pregnancy, clinically significant increase in suicidal ideation (plan or intent) or significant worsening of depression, newly arising clinically significant abnormal laboratory tests, or any clinically significant, uncontrolled, or unstable medical or surgical condition that could affect the patient's ability to participate in the study or potentially compromise the patient's well-being during the study.
5. The patient does not require treatment with a potent (strong) cytochrome P450 subtype 3A4 (CYP3A4) inhibitor, or St. John's wort.
6. The patient is willing to refrain from use of all other formulations of cyclobenzaprine for the duration of the study.
7. The patient is willing to refrain from use of monoamine oxidase inhibitors for the duration of the study.
8. Female patients of childbearing potential continue to agree to practice one of the medically acceptable methods of birth control detailed in the lead-in study.

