7.3. Patient Exclusion Criteria

There are no exclusion criteria for this study.

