8.5. Concomitant Medications

Many of the restrictions in the lead-in study related to concomitant medications and trauma-focused psychotherapy will be relaxed. Therefore, patients may utilize particular antidepressants, mood stabilizers, anticonvulsants, benzodiazepines, stimulants, and opioids, if needed. Patients may take medications to help them sleep, per the judgment of the investigator.

Any concomitant medications or other treatments, including dietary supplements, must be recorded in the patient's medical record and case report form along with the indication, dose and dates of treatment.

The following medications are specifically excluded during the study and patients must agree to refrain from use of these medications during the study:

- Any other forms of cyclobenzaprine (FLEXERIL®, AMRIX®, FEXMID®, or generic equivalents) continue to be specifically excluded during the study and patients must agree to refrain from use of these medications during the study.
- Monoamine oxidase inhibitors (tranylcypromine, phenelzine, isocarboxazid, and selegiline)
- Cytochrome P450 3A4 inhibitors (strong ones) (refer to [Appendix 2](#) for a list).
- St. John's wort

NOTE: Patients initiating treatment with antidepressants, tramadol or other opioids, triptans, or any other serotonergic medication should be cautioned about the possibility of serotonin syndrome which has been reported in patients receiving cyclobenzaprine with selective serotonin reuptake inhibitors (SSRIs), serotonin–norepinephrine reuptake inhibitors (SNRIs) and related agents. (See [Appendix 3](#), AMRIX® Package Insert, Warnings Section). The patient should be instructed to call the clinic immediately in the event of any of the warning signs or symptoms of serotonin syndrome, as outlined in the informed consent. The investigator should carefully review the patient's complete list of medications when considering new treatments and the site should ask the patient to call the site (or return for an unscheduled clinic visit) within one week after adding a new serotonergic therapy (or increasing the dose of a prior treatment).

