APPENDIX 3. AMRIX® PACKAGE INSERT (DATED MAY 2016)

HIGHLIGHTS OF PRESCRIBING INFORMATION

These highlights do not include all the information needed to use AMRIX safely and effectively. See full prescribing information for AMRIX.

AMRIX® (cyclobenzaprine hydrochloride extended-release capsules), for oral use
Initial U.S. Approval: 1977

RECENT MAJOR CHANGES

Dosage and Administration (2) 05/2016

INDICATIONS AND USAGE

AMRIX is a muscle relaxant indicated as an adjunct to rest and physical therapy for relief of muscle spasm associated with acute, painful musculoskeletal conditions (1)

Limitations of Use:

- AMRIX should be used only for short periods (up to 2 or 3 weeks) (1)
- AMRIX has not been found effective in the treatment of spasticity or cerebral palsy (1)

DOSAGE AND ADMINISTRATION

- Recommended adult dose for most patients is 15 mg taken once daily. Some patients may require 30 mg taken once daily. (2)
- Recommended to take doses at approximately same time each day (2)
- Instruct patients to swallow AMRIX capsules intact or to sprinkle capsule contents on a tablespoon of applesauce and swallow immediately without chewing. (2)
- Use for periods longer than 2 or 3 weeks is not recommended (2)

DOSAGE FORMS AND STRENGTHS

- Extended-release capsules: 15 and 30 mg (3)

CONTRAINDICATIONS

- Hypersensitivity to any component of this product (4)
- Concomitant use of monoamine oxidase (MAO) inhibitors or within 14 days after their discontinuation (4)
- During acute recovery phase of myocardial infarction, and in patients with arrhythmias, heart block or conduction disturbances, or congestive heart failure (4)
- Hyperthyroidism (4)

FULL PRESCRIBING INFORMATION: CONTENTS*

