4 CONTRAINDICATIONS

- Hypersensitivity to any component of this product. These adverse reactions may manifest as an anaphylactic reaction, urticaria, facial and/or tongue swelling or pruritus. Discontinue AMRIX if a hypersensitivity reaction is suspected.
- Concomitant use of monoamine oxidase (MAO) inhibitors or within 14 days after their discontinuation. Hyperpyretic crisis seizures and deaths have occurred in patients receiving cyclobenzaprine (or structurally similar tricyclic antidepressants) concomitantly with MAO inhibitor drugs.
- During the acute recovery phase of myocardial infarction, and in patients with arrhythmias, heart block or conduction disturbances, or congestive heart failure.
- Hyperthyroidism.

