17 PATIENT COUNSELING INFORMATION

See FDA-approved patient labeling (Patient Information).

- Instruct patients to swallow AMRIX capsules intact or to sprinkle capsule contents on a tablespoon of applesauce and swallow immediately without chewing.
- Advise patients to stop taking AMRIX and to notify their physician right away if they experience symptoms of an allergic reaction, such as difficulty breathing, hives, swelling of face or tongue, or itching.
- Advise patients that AMRIX should not be taken with MAO inhibitors or within 14 days after their discontinuation.
- Caution patients about the risk of serotonin syndrome with concomitant use of AMRIX and other drugs, such as SSRIs, SNRIs, TCAs, tramadol, bupropion, meperidine, verapamil, or MAO inhibitors. Advise patients of the signs and symptoms of serotonin syndrome [see Warnings and Precautions (5.1)] and instruct patients to seek medical care immediately if they experience these symptoms.

AMRIX® (cyclobenzaprine hydrochloride extended-release capsules)

- Advise patients to stop taking AMRIX and to notify their physician right away if they experience arrhythmias or tachycardia.
- Advise patients that AMRIX may enhance the impairment effects of alcohol. These effects may also be seen if AMRIX is taken with other CNS depressants.
- Caution patients about operating an automobile or other hazardous machinery until it is reasonably certain that AMRIX therapy will not adversely affect their ability to engage in such activities.
- Advise patients to take AMRIX at approximately the same time each day.

TEVA CNS

Distributed By:
Teva Pharmaceuticals USA, Inc.
North Wales, PA 19454

Manufactured By:
Adare Pharmaceuticals, Inc.
Vandalia, OH 45377
AMR-008

US Patent Nos. 7387793, 7754372, 7790199, 7820203, 7829121

AMRIX is a trademark of Teva Pharmaceuticals International GmbH, or its affiliates. © 2004-2016 Teva Pharmaceuticals USA, Inc.
All rights reserved.

Patient Information

**AMRIX® (am-rix)
(cyclobenzaprine hydrochloride)
Extended Release Capsules**

Read this Patient Information before you start taking AMRIX and each time you get a refill. There may be new information. This information does not take the place of talking with your healthcare provider about your medical condition or your treatment.

What is AMRIX?

AMRIX is a prescription medicine used along with rest and physical therapy to help treat muscle spasm due to acute, painful musculoskeletal problems.

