AMRIX should only be used for up to 2 or 3 weeks. It is not known if AMRIX is effective when used for longer periods.

It is not known if AMRIX is safe and effective in children.

Who should not take AMRIX?

Do not take AMRIX if you:

- are allergic to cyclobenzaprine or any of the ingredients in AMRIX. See the end of this Patient Information leaflet for a complete list of ingredients in AMRIX.

Talk to your healthcare provider or get medical help right away if you have symptoms of an allergic reaction such as:

- difficulty breathing
- hives
- swelling of your face or tongue
- itching
- are taking certain antidepressants, known as monoamine oxidase (MAO) inhibitors or it has been 14 days or less since you stopped taking a MAO inhibitor. Ask your healthcare provider or pharmacist for a list of these medicines if you are not sure.
- have had a recent heart attack
- have heart rhythm problems (arrhythmias)
- have heart failure
- have an overactive thyroid (hyperthyroidism)

Talk to your healthcare provider before taking this medicine if you have any of the conditions listed above.

What should I tell my healthcare provider before taking AMRIX?**Before you take AMRIX, tell your healthcare provider if you:**

- have a history of eye problems including glaucoma
- have heart problems or have had a heart attack
- have liver problems
- have trouble emptying your bladder (urinary retention)
- are pregnant or plan to become pregnant. It is not known if AMRIX will harm your unborn baby.

AMRIX® (cyclobenzaprine hydrochloride extended-release capsules)

- are breastfeeding or plan to breastfeed. It is not known if AMRIX passes into your breast milk. You and your healthcare provider should decide if you will take AMRIX or breastfeed.

AMRIX may affect the way other medicines work, and other medicines may affect how AMRIX works.

Tell your healthcare provider about all the medicines you take including prescription and non-prescription medicines, vitamins, and herbal supplements.

Especially tell your healthcare provider if you take:

- a medicine to treat depression, mood, anxiety, psychotic or thought disorders
- a pain medicine called tramadol or meperidine
- barbiturates or other medicines that depress your central nervous system (CNS depressants)
- a medicine that prevents nerve impulses (anticholinergic medicines)
- a medicine to help quit smoking called bupropion
- a blood pressure medicine called verapamil

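### P303 entry rules bar MAO inhibitors only from entry onward and omit the 14-day period after stopping that the protocol's own appended label contraindicates

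*Protocol*

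**What the plan says.** Criterion 7 in Protocol section 7.2, repeated in the synopsis, is "The patient is willing to refrain from use of monoamine oxidase inhibitors for the duration of the study". Section 8.5 names the MAO inhibitors in a list introduced by "The following medications are specifically excluded during the study and patients must agree to refrain from use of these medications during the study" and gives no interval since stopping. Section 7.3 states "There are no exclusion criteria for this study".

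Sections 6.1 and 9.1.4 start dosing on the evening of Visit 1. Section 9.1.2 intends Visit 1 to coincide with the final lead-in visit. In extenuating circumstances it allows a gap of up to 14 days with the lead-in assessments reused, and a longer gap if baseline assessments are repeated.

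Appendix 3 reproduces the label of an oral extended-release cyclobenzaprine product. Its section 4 lists as a contraindication "Concomitant use of monoamine oxidase (MAO) inhibitors or within 14 days after their discontinuation". Its counselling section says "Advise patients that AMRIX should not be taken with MAO inhibitors or within 14 days after their discontinuation". Its patient leaflet tells patients not to take the drug if "it has been 14 days or less since you stopped taking a MAO inhibitor".

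**The concern.** Criterion 7 and section 8.5 look only forward from entry. The label contraindicates two things: taking the drugs together, and starting cyclobenzaprine too soon after an MAO inhibitor is stopped. P303's written rules cover only the first.

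A site that applies the entry criteria exactly as written could therefore give the first dose at a time when the protocol's own appendix says cyclobenzaprine is contraindicated. Dosing begins the same evening as Visit 1, so no washout is built in. Patients who had placebo in the lead-in would be taking their first study dose of cyclobenzaprine.

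Label section 4 reports hyperpyretic crisis, seizures and deaths. It reports them for concomitant use and gives no event data for the 14 days after stopping, although it applies the contraindication to both.

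**Working it through.** The plan states no figure on this point. The check has two parts: whether any P303 rule closes the gap, and what the fix would do to dosing dates.

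**1. Each entry criterion, for a patient who stopped an MAO inhibitor within 14 days before the first P303 dose**

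| Criterion (section 7.2) | Subject | Failed because of the MAO inhibitor use? |
|---|---|---|
| 1 | Lead-in completion and compliance | No |
| 2 | Consent | No |
| 3 | Lead-in entry requirements were met | Not on P303's wording; the lead-in text is not available |
| 4 | Intervening medical conditions during the lead-in | Not by the drug use itself |
| 5 | Strong CYP3A4 inhibitors, St. John's wort | No |
| 6 | Other cyclobenzaprine formulations | No |
| 7 | Future MAO inhibitor use | No |
| 8 | Contraception | No |

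There are no exclusion criteria to add. The body of the protocol cites Appendix 3 for serotonin syndrome (8.5) and pregnancy category (11.4), not for this interval. The other 14-day period in the protocol (6.1, 9.1.2, 10.2) concerns reuse of baseline assessments. SAP section 3.1 adds no criteria and refers back to the protocol.

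**2. Effect of a 14-day look-back on the first dose**

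Let day 0 be the final lead-in visit and *s* the day of the last MAO inhibitor dose. Reading the leaflet's limit literally, 14 days after stopping is still too early, so

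earliest first P303 dose = max(*s* + 15, 0).

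Under sections 6.1 and 9.1.2, baselines are repeated only if more than 14 days have passed.

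| *s* | Earliest first dose | Repeat baselines? |
|---|---|---|
| −15 | −15 + 15 = day 0 (no delay) | No |
| −14 | −14 + 15 = day 1 | No |
| −1 | −1 + 15 = day 14 | No |
| 0 | 0 + 15 = day 15 | Yes |
| 1 | 1 + 15 = day 16 | Yes |

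Use that ended 1 to 14 days before the final lead-in visit therefore costs a delay of 1 to 14 days against same-day rollover. Use that ended on or after that visit puts the first dose at day 15 or later, with baselines repeated.

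These figures describe the effect of the fix. They do not measure how often the problem arises or how much harm it does.

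**The case against.** P303 is an extension and leans on documents we do not have. Criterion 3 refers to the lead-in entry requirements, and section 4 makes the lead-in protocol and Investigator's Brochure relevant. With same-day rollover the whole look-back falls inside the lead-in, whose own medication rules may have barred these drugs. Section 8.5 says many lead-in restrictions are relaxed in P303, so the lead-in was generally stricter. P303 also leaves out the label's cardiac and thyroid contraindications, which suggests that contraindications were left to the lead-in. This is why the point is limited to what P303 itself says. It does not remove the point: criterion 3 concerns requirements already met for the lead-in and does not plainly reach use late in that study or in a gap after it. P303 also chose to write an MAO inhibitor criterion, and wrote half of it.

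The scenario is narrow. A lead-in active patient who used an MAO inhibitor late in that study had already taken the combination, so preventable first exposure is mainly in former placebo patients. That is correct and keeps the point small.

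Safeguards exist: the suitability interview (7.1), the Visit 1 medication review (9.1.4), the duty in 8.5 to record concomitant treatments "along with the indication, dose and dates of treatment", the investigator's duty to know the drug's risks (14.1), and the label text itself. None is an eligibility rule. The Visit 1 review covers new and continuing medications, so a drug already stopped is not clearly captured, and SAP section 11.1 expects no new prior medications in P303.

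The label is for 15 to 30 mg taken orally, not 5.6 mg sublingually. That stands, although the sponsor appended it and refers to it for safety information.

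**Conclusion.** The concern holds as a statement about P303's written rules: nothing in its entry criteria or section 8.5 excludes a patient who stopped an MAO inhibitor within 14 days before the first dose, although Appendix 3 contraindicates cyclobenzaprine then.

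The importance is minor. Frequency should be very low and cannot be quantified, because the documents give no rate of MAO inhibitor use or of delayed entry. No analysis is affected.

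The conclusion assumes that the appended label is a fair guide for the sublingual product. It does not claim that the programme lacks a look-back, since the lead-in protocol and the Investigator's Brochure may contain one.

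**What to change.** Reword criterion 7 in section 7.2 and the synopsis along these lines: *the patient has taken no monoamine oxidase inhibitor in the 14 days before the first dose of P303 study drug and agrees to take none until the study ends.* In section 8.5, extend the MAO inhibitor bullet to cover the same 14 days.

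Because the Visit 1 review may miss a drug already stopped, the site should ask about it, with the stop date, at the interview that section 7.1 already requires. No new visit or assessment is needed.

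The cost is one clause in three places in a protocol amendment, and an occasional patient delayed or not enrolled. During a delay of 1 to 14 days, a lead-in active patient would be off drug while the on-drug Week 12 scores remain the P303 baseline. Section 9.1.2 already permits a gap of that length. Where baselines are repeated, SAP section 7.1 accommodates it, since it takes the last non-missing value before the first P303 dose.

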7.3. Patient Exclusion Criteria

There are no exclusion criteria for this study.

7.4. Withdrawal Criteria

In accordance with the Declaration of Helsinki, human patients have the right to withdraw from the study at any time for any reason. The investigator and Tonix also have the right to remove patients from the study. Additional information regarding withdrawal or discontinuation of patients is described in detail in [Section 9.5](#).

8. STUDY DRUG MATERIALS AND MANAGEMENT

8.1. Study Drug Packaging, and Labeling and Storage

The study medication bottles will be labeled minimally with the following information: study number TNX-CY-P303, sponsor name and address, bottle number, drug name, quantity, storage conditions, usage instructions, and caution statements for investigational new drug, i.e., Caution: New Drug Limited by United States Law to Investigational Use, and Keep Out of Reach of Children and Pets.

Each study medication bottle will contain 40 tablets. Since the patient will dose with two tablets sublingually each night, two bottles will be dispensed to each patient at Visit 1 (baseline), Visit 3 (Week 4) and Visit 4 (Week 8); this will provide the patient with 80 tablets to cover the 4 weeks of dosing between visits, plus additional tablets to cover loss and/or visit window variability. The patient should be instructed to take all the tablets in one bottle before opening the second bottle. The patient should be instructed to keep this study medication in a safe location out of extreme environmental conditions and out of the reach of children and pets, and be instructed that this medication is not to be taken by any individual other than the study patient. Each patient will also be instructed that they will be expected to return both bottles and all unused study medication at each clinic visit; unused medication will be counted to assess compliance with study drug treatment.

Storage of the study drug at the investigational site should be under locked and secure conditions with limited staff access. Study drug should be stored at 20-25°C/68-77°F in a temperature/humidity-monitored room; however, brief excursions 15-30°C/59-86°F are permitted with sponsor's approval.

8.2. Dosing Instructions

Patients will be instructed to take two (2) TNX-102 SL 2.8 mg tablets sublingually, placed simultaneously under the tongue, each evening at bedtime starting on evening of Day 0 and continuing without interruption for 12 weeks. The study drug should be taken at bedtime after teeth brushing and other oral care has been completed. The mouth/sublingual area should be moist at the time of dosing, so the patient should drink a few sips of water prior to dosing, especially if prone to dry mouth. Patients will be instructed to place the two TNX-102 SL 2.8 mg tablets under their tongue and keep them there until they have dissolved. They should not swallow, crush or chew the tablets. Patients should not eat or drink (or chew gum) for at least 15 minutes after dosing, and preferably not until morning. Patients will be reminded that only two (2) tablets are allowed per day. Note: In the event that the patient misses a dose, instruct the patient to continue dosing with two (2) tablets the next evening; i.e., they should not take more to make up for the missed dose.

8.3. Dispensing Instructions

Each enrolled patient will be assigned 2 bottles of TNX-102 SL at each dispensing visit. Bottles of TNX-102 SL tablets will be supplied to sites as open stock.

8.4. Release of Clinical Study Supplies to the Investigator

Tonix or Tonix's designee's standard operating procedures for releasing clinical trial supplies to the site will be followed.

8.5. Concomitant Medications

Many of the restrictions in the lead-in study related to concomitant medications and trauma-focused psychotherapy will be relaxed. Therefore, patients may utilize particular antidepressants, mood stabilizers, anticonvulsants, benzodiazepines, stimulants, and opioids, if needed. Patients may take medications to help them sleep, per the judgment of the investigator.

Any concomitant medications or other treatments, including dietary supplements, must be recorded in the patient's medical record and case report form along with the indication, dose and dates of treatment.

The following medications are specifically excluded during the study and patients must agree to refrain from use of these medications during the study:

- Any other forms of cyclobenzaprine (FLEXERIL®, AMRIX®, FEXMID®, or generic equivalents) continue to be specifically excluded during the study and patients must agree to refrain from use of these medications during the study.
- Monoamine oxidase inhibitors (tranylcypromine, phenelzine, isocarboxazid, and selegiline)
- Cytochrome P450 3A4 inhibitors (strong ones) (refer to [Appendix 2](#) for a list).
- St. John's wort

NOTE: Patients initiating treatment with antidepressants, tramadol or other opioids, triptans, or any other serotonergic medication should be cautioned about the possibility of serotonin syndrome which has been reported in patients receiving cyclobenzaprine with selective serotonin reuptake inhibitors (SSRIs), serotonin–norepinephrine reuptake inhibitors (SNRIs) and related agents. (See [Appendix 3](#), AMRIX® Package Insert, Warnings Section). The patient should be instructed to call the clinic immediately in the event of any of the warning signs or symptoms of serotonin syndrome, as outlined in the informed consent. The investigator should carefully review the patient's complete list of medications when considering new treatments and the site should ask the patient to call the site (or return for an unscheduled clinic visit) within one week after adding a new serotonergic therapy (or increasing the dose of a prior treatment).

